In general, outcome variables with repeated measurements will be analysed by fitting linear mixed models (for continuous outcomes or outcomes treated as continuous, such as 5-point Likert scales) or (for categorical / binary outcomes) generalised linear mixed models (GLMMs) or generalised additive mixed models (GAMMs), with fixed effects for treatment and time, and their interaction, and random effects for subjects and assessments within subjects, using restricted maximum likelihood (REML) or similar algorithms. These models allow missing values to be accommodated.

These methods will allow the most suitable variance-covariance model for the repeated measures to be selected, using Akaike's Information Criterion, and, if appropriate, commonality of nonlinear trends over time to be explored via splines. The F-test (or equivalent chi square test, t-test of coefficients in logistic regression) will be used to test for an overall group by time interaction in outcomes measured at all three follow-up times (0, 4 and 12 weeks).

Outcomes measured at two or fewer time points

For outcome variables measured at two or fewer time-points, different models will be used, depending on the nature of the outcome variable:

- Where the outcome is binary and proportions are required, a test of change in proportions for categorical outcomes, e.g. the Cochran-Mantel-Haenszel test, will be applied or, if covariates are required in the analysis, logistic regression with random effects for subjects. Such logistic regression models are instances of GLMMs or GAMMs.
- 2. For continuous outcomes or outcomes treated as continuous (such as 5-point Likert scales) linear mixed models will be used (as for outcomes measured at three time-points).
- 3. In simple cases of the preceding points, the analysis may reduce to (in the sense of being equivalent to) a test of whether there is a difference between the two groups (treatment and control) in the changes in the mean (for continuous outcomes). If just one time point is involved, we may use a binomial test of proportions (for categorical outcomes).

Outcomes measured at 4 and 12 weeks but without a baseline measurement will be covered by this case.

Missing values

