The primary outcome of this repeated measures RCT is the proportion of participants accurately identifying alcohol as a clear risk factor for breast cancer at 4-weeks post-randomisation. Inferences about the effect of the Health4Her intervention on the primary outcome will be based on a comparison, between treatment groups, of change from baseline to 4-weeks post-randomisation using a Cochran-Mantel-Haenszel test. This analysis tests for homogeneity of the odds ratio across strata (i.e. intervention and control). A binomial test (that is, a test of proportions) will be used as an ancillary analysis of the primary outcome (i.e. the difference in proportions between the two groups at 4-weeks post-randomisation).

Relevant covariates (from the list of potential covariates below) may also be used in further analysis, using generalised linear models (logistic regression) to make comparisons. Additional analyses may use covariates for post-stratification.

Secondary Outcomes

Alcohol Consumption

Alcohol consumption will be assessed by the Alcohol 14-day Timeline Follow-back (TLFB). Heavy drinking days are measured as >40 grams of alcohol (>4 Australian standard drinks). Alcohol consumption will also assessed by the AIHW alcohol frequency quantity items. Assessments are made at 0, 4 and 12 weeks and linear mixed models (continuous variables) or GLMMs or GAMMs (categorical / binary variables) will be used. The following outcomes will be analysed (transformed if necessary for analysis):

Secondary outcome 1 – Proportion of participants drinking less than or equal to 10 standard drinks per week at 4-weeks and 12-weeks post-randomisation. Derived from (operationalised in two ways):

- Has the participant consumed >10 standard drinks in week one AND/OR >10 standard drinks in week two? (tlfb_nhmrc_both_comprh)
- Has the participant consumed >10 standard drinks in both week one AND week two? (derived variable: tlfb_nhmrc_bothwks)

Secondary outcome 2 – Proportion of participants drinking less than or equal to 10 standard drinks per week at 4-weeks and 12-weeks post-randomisation, among only participants who drink more than 10 standard drinks per week at baseline.

Subgroup defined as either i. women who consumed >10 standard drinks in week one AND/OR >10 standard drinks in week two (tlfb_nhmrc_both_comprh) or ii. women who consumed >10 standard drinks in both week one AND week two (tlfb_nhmrc_bothwks).

Outcome derived from:

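### For the three-visit yes/no drinking outcome, the SAP borrows a linear-model specification: one variance cannot be estimated in practice, and the REML wording leaves room for shrunken odds ratios

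*SAP*

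**What the plan says.** The SAP section on outcomes with more than two time points sets one specification for every repeated outcome. Continuous outcomes get linear mixed models. The binary case is "for categorical / binary outcomes) generalised linear mixed models (GLMMs) or generalised additive mixed models (GAMMs". Both share the same random effects and estimator: "random effects for subjects and assessments within subjects, using restricted maximum likelihood (REML) or similar algorithms". The next paragraph selects the variance-covariance model by Akaike's criterion (AIC), and an F-test or equivalent "will be used to test for an overall group by time interaction in outcomes measured at all three follow-up times (0, 4 and 12 weeks").

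Under Secondary Outcomes, Alcohol Consumption, the SAP applies this to drinking: "Assessments are made at 0, 4 and 12 weeks and linear mixed models (continuous variables) or GLMMs or GAMMs (categorical / binary variables) will be used". Secondary outcome 1 is binary and has two definitions, the first being "Has the participant consumed >10 standard drinks in week one AND/OR >10 standard drinks in week two? (tlfb_nhmrc_both_comprh"). Each definition yields one value per woman per visit.

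Two other SAP rules differ. Binary outcomes at two or fewer time points that need covariates get "logistic regression with random effects for subjects. Such logistic regression models are instances of GLMMs or GAMMs", with no assessment-level effect. The primary outcome compares "change from baseline to 4-weeks post-randomisation using a Cochran-Mantel-Haenszel test", so no mixed model is involved; secondary outcome 6 is handled the same way.

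The SAP's software section allows GenStat, R, SAS or STATA and names no procedure. Neither document names a likelihood approximation for binary mixed models, or says whether a reported odds ratio is subject-specific or marginal.

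**The concern.** In a linear mixed model the assessment-within-subject term is the residual, and REML is the standard estimator. Neither carries over to a yes/no outcome seen once per visit.

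- **The extra variance.** A Bernoulli response has no separate residual variance. With one response per visit, the data say almost nothing about how much visit-level variation to add on the logit scale. The fitted odds ratio nevertheless depends on that amount.
- **The estimator.** REML is defined for linear models. Its usual binary counterpart is a linearised fit (penalised quasi-likelihood, PQL), which pulls coefficients towards zero when each woman contributes few binary observations and women differ strongly.

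The reported estimates are what is at stake. Protocol 14.2 promises 95% confidence intervals throughout. Protocol 14.1 says this pilot will inform a multicentre trial and lists drinking within guidelines among its effectiveness markers. With four packages allowed and no estimator named, two analysts following the SAP could report materially different odds ratios from the same data.

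**Working it through.** **1. The plan's own figure.** The documents give no calculation for the mixed model; the only planning figure is for the primary endpoint (protocol 14.1: 0.22 versus 0.34, two-sided 0.05, 80% power, 20% attrition).

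n per arm = [1.960·√(2·0.28·0.72) + 0.8416·√(0.22·0.78 + 0.34·0.66)]² / 0.12² = (1.2445 + 0.5296)² / 0.0144 = 218.6, so 219.

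219 / 0.80 = 273.75, so 274 per arm and 548 in total. This matches the protocol. It does not bear on the mixed model.

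**2. Inputs for the mixed model.**
- From the documents: two arms; visits at 0, 4 and 12 weeks; 558 randomised, 279 per arm (SAP, study rationale and design); 20% attrition, giving 558 × 0.80 ≈ 446 completers, 223 per arm.
- Assumed, because the documents do not give them: 65% or 80% of women within the limit; between-woman SD of 1 to 4 on the logit scale; true group-by-time odds ratio of 2.00 (log 0.693) at both follow-ups; no assessment-level variation.

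Model: logit P(within limit) = arm-by-visit mean + uᵢ, with uᵢ ~ N(0, SD²).

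**3. Can the assessment-level SD be estimated?** Using expected cell counts at N = 558, the model was refitted by maximum likelihood with that SD held at 1, 2 or 3. The ranges run over both proportions and all four between-woman SDs.

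| Imposed SD (truth 0) | Fitted odds ratio (truth 2.00) |
|---|---|
| 1 | 2.21–2.26 |
| 2 | 2.83–2.97 |
| 3 | 3.87–4.16 |

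The deviance rose by only 0.002 to 0.070 across all of these, against 3.84 for a 5% test. The data cannot choose between fits whose odds ratios differ about twofold. Under maximum likelihood the superfluous effect inflates the odds ratio.

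**4. What does a linearised REML fit do?** Same data, random intercept per woman only:

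| Between-woman SD | Quadrature ML odds ratio | Linearised REML odds ratio | Share of true log odds ratio | Shrinkage |
|---|---|---|---|---|
| 1 | 2.00 | 1.83–1.86 | 0.87–0.89 | 11–13% |
| 2 | 2.00 | 1.65–1.67 | 0.72–0.74 | 26–28% |
| 3 | 2.00 | 1.54–1.55 | 0.62–0.63 | 37–38% |
| 4 | 2.00 | 1.46 | 0.55 | 45% |

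For example, at SD 2 and 80% within limit, 0.513 / 0.693 = 0.74. When the assessment-level effect was added to the linearised fit, its variance went to 0 and the log odds ratio did not change. Shrinkage therefore comes from the linearisation.

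**5. Does the test suffer?** 150 simulated trials per setting, 446 completers, 80% within limit, one group-by-time coefficient:

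| SD | Quadrature ML: mean / SD | Linearised REML: mean / SD |
|---|---|---|
| 2 | 0.701 / 0.458 = 1.53 | 0.517 / 0.332 = 1.56 |
| 3 | 0.630 / 0.480 = 1.31 | 0.396 / 0.299 = 1.32 |

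With no true effect, all means lay between 0.025 and 0.036. Estimate and spread shrink together, so the signal-to-noise ratio hardly moves. This check uses the spread across trials, not each fit's own standard error, and a single coefficient, not the joint test over both follow-ups.

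**6. Intervals.** Coverage depends on the true effect. With 223 women per arm, 70% within the limit and SD 3.5 (all but the number per arm assumed), nominal 95% intervals from the linearised fit covered the truth in about 93% of trials at odds ratio 2, 81% at 3 and 58% at 5.

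**The case against.** The SAP does not require a linearised fit. It allows similar algorithms and the most suitable procedure in four packages, and all of them leave room for a likelihood fit. It also selects the covariance model by AIC. AIC needs a true likelihood, which a linearised fit does not supply, and it charges 2 per parameter. An assessment-level effect that gains almost nothing in deviance would normally be dropped. The SAP's two-visit rule already uses subject effects alone. **This stands.** A careful analyst can reach a sound model within the text, so shrinkage is a risk left open and not a predicted result. What remains is that the named random effects and the named estimator are both poor for these data, and nothing in the SAP tells the analyst to depart from them.

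A reader might infer several stronger points that do not hold:

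- **That the assessment-level effect causes the shrinkage.** It does not. Under maximum likelihood it inflates the odds ratio; under the linearised fit it drops out.
- **That its variance is strictly unidentified.** With a logit link it is formally identified through the shape of the link alone. Not estimable in practice is the accurate description.
- **That the trial's main inference is at risk.** The primary outcome and secondary outcome 6 use Cochran-Mantel-Haenszel tests, and the group-by-time test is little affected.
- **That secondary outcome 2 is the same case.** It is limited to women above 10 drinks per week at baseline. When subgroup and outcome use the same definition, every woman has the same baseline value and only two visits carry information. The figures above do not describe it.

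It is also fair to say that the SAP states secondary outcome 1 as a proportion and does not name an odds ratio as the reported effect.

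**Conclusion.** The point holds as a specification problem in a secondary analysis, chiefly secondary outcome 1. Read literally, the SAP asks for a variance that these data cannot supply: at most 0.070 deviance units at N = 558, with the odds ratio moving from 2.00 to about 2.2–4.2 if the effect is forced in. A linearised REML fit, if chosen, could shrink the log odds ratio by about 11% to 45%.

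These sizes rest on the assumed between-woman SD, proportion within the limit and true odds ratio. No document supports a particular SD, so the whole range should be read as possible. Interval coverage may be near nominal for a modest effect and poor for a large one. It would go too far to say that the odds ratios will be too small, or that the tests are invalid. This is a cheap improvement, not an error that undermines the trial.

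**What to change.** For binary outcomes measured at all three visits:

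- Specify a logistic model with arm, visit and their interaction and a single random intercept per woman, fitted by maximum likelihood with adaptive Gauss-Hermite quadrature.
- Delete the assessment-within-subject effect and REML for these outcomes. Keep both for the linear mixed models.
- Report model-based proportions by arm and their difference at 4 and 12 weeks, with 95% intervals, averaging over the fitted random-intercept distribution. State that any odds ratio is subject-specific.
- For secondary outcome 2, where the subgroup definition makes the baseline value the same for every woman, model only the 4- and 12-week visits.

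Ordinary GEE is not a free substitute. It is not generally valid under the missing-at-random assumption in the SAP's missing values section, and it targets a marginal odds ratio.

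The cost is a few sentences in the SAP, slightly longer run time and possibly some convergence checks. The method is routine in R, SAS and STATA, which the SAP already lists.

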Secondary outcome 6 – Proportion of participants accurately identifying i) the amount of alcohol in an Australian standard drink; ii) the number of standard drinks in an average restaurant serve of red wine; iii) the maximum number of standard drinks per week recommended by current Australian alcohol guidelines, at 4-weeks post-randomisation).

Analyses will be the comparison, between treatment groups, of change from baseline to 4-weeks post-randomisation using a Cochran-Mantel-Haenszel test. Relevant covariates (from the list of potential covariates below) may also be used in further analysis, using generalised linear models (logistic regression) to make comparisons. Additional analyses may use covariates for post-stratification. A binomial test (that is, a test of proportions) may be used as an ancillary analysis of the outcome (i.e. the difference in proportions between the two groups at 4-weeks post-randomisation), with logistic regression as an option if covariates are employed.

Outcome derived from:

- Proportion of participants who accurately respond to "In Australia, a standard drink contains
 ____ grams of alcohol" knowl_sd = 1 (10 grams)
 - recode to binary variable (1 = accurate | 2 = not accurate)
- Proportion of participants who accurately respond to "An average restaurant serve of red wine contains..." knowl_redwine = 3 (1.6 standard drinks)
 - recode to binary variable (1 = accurate | 2 = not accurate)
- Proportion of participants who accurately respond to "According to the latest Australian alcohol guidelines, it is recommended that healthy women should drink no more than _______standard drinks per week." knowl_alcguideline = free-text response of "10"
 - recode to binary variable (1 = accurate | 2 = not accurate)

Secondary outcome 7 – Proportion of participants who have accessed health information on i) alcohol harms, ii) alcohol and breast cancer risk, and iii) alcohol harm-reduction.

A binomial test (that is, a test of proportions) will be used (i.e. the difference in proportions between the two groups at 12-weeks post-randomisation), with logistic regression as an option if covariates are employed.

Outcome derived from info_sought_catg = 1 (alcohol) and/or 2 (alcohol and breast cancer risk) and/or 3 (alcohol and other health risks) and/or 4 (alcohol and women's health)

- recode to binary variable (1 = accessed | 2 = did not access)

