## 6 RANDOMISATION AND BLINDING

Women who consent to participate will complete a quick demographic questionnaire and a series of brief measures (evaluating alcohol use, alcohol literacy, quality of life and general health) administered by Researcher 1 or partially self-completed if the Researcher is helping another participant, before being provided with an iPad and randomised at a 1:1 ratio (using computer sequenced block randomisation) to receive the computerised active or control condition.

Randomisation will use a standard computer generated "permuted blocks of variable size" scheme for each stratum. Randomisation lists for each stratum will be generated at the start of the study by the data scientist assisting with the development of the iPad intervention and linked to a unique identification code. The data scientist will play no other role in the randomisation. Randomisation will be linked to a unique identification code, which will be in a re-identifiable format.

Participants will be informed that the study is concerned with promoting health across a range of lifestyle factors (e.g. alcohol use, diet/exercise), which accurately corresponds to the planned outcome measures and intervention conditions and therefore will blind participants to group allocation. Intervention and control computer tasks will be visually identical and will be self-paced. The study researcher performing outcome assessments (Researcher 2) is expected to remain blind to trial allocation.

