## 14 STATISTICAL METHODS

### 14.1 Sample Size Estimation

Since the aims of this pilot RCT include preliminary hypothesis testing for effectiveness, a power and sample size calculation has been performed (Moore, Carter et al. 2011). Power and sample size estimates were carried out using PS: Power and Sample Size Calculation V3.1.2 (Dupont and Plummer 1990), assuming a type 1 error probability of  $\alpha < 0.05$ , 2-tailed, and equal-sized groups. Power calculations are based on the primary endpoint, proportion of participants who accurately identify alcohol as a clear risk factor for breast cancer.

Our sample size estimation is based on our previous online survey study with 391 women who have attended/are eligible to attend breast screening services (Health4Her Phase I). If the proportion of control participants who accurately identify alcohol as a clear risk factor for breast cancer is 0.22 and the true response rate for participants receiving the alcohol brief intervention is 12% greater at 0.34, and compensating for 20% attrition at follow-up, then 548 participants (274 per arm) will provide power of 80% to be able to reject the null hypothesis.

Given the lack of definitive evidence regarding alcohol BI effects in women, and particularly women of middle- and older-age in a breast screening setting, this powered pilot RCT will inform the development of a subsequent, comprehensive multicentre trial. This pilot RCT will generate preliminary data on intervention response using exploratory surrogate/proximal markers of effectiveness (e.g. proportion of participants accurately identifying alcohol as a breast cancer risk factor, proportion of participants drinking within guidelines, alcohol consumption and well-being), and will provide concrete estimates of risky alcohol consumption prevalence, and expected rates of missing data and participant attrition specific to the population under study (Moore, Carter et al. 2011).

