### 14.2 Statistical Analysis Plan

A detailed statistical analysis plan will describe the statistical methods for each outcome as well as how missing data will be dealt with. Data will be collated, cleaned and validated, using programmed edit checks, in a database that will be locked prior to analyses. All statistical tests will be two-tailed, with alpha level set to 0.05. Statistical analyses will be adjusted for multiple comparisons when indicated. 95% confidence intervals will be reported throughout. All randomised participants will be included in the analysis (i.e. intention-to-treat) for primary and secondary outcomes. Demographic characteristics (e.g. age) and baseline measurements (e.g. knowledge of alcohol as a clear risk factor for breast cancer, alcohol consumption) will be summarised and reported by intervention arm. The analyses will examine change in outcomes over time (4-weeks and/or 12-weeks) relative to baseline. The complete details of the analyses will be specified in a Statistical Analysis Plan that will be reviewed and approved by a study team prior to database lock. Analyses will be conducted using the most appropriate procedures in R and STATA.

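### The SAP does not define the table behind its test of change for the primary outcome; on the one arms-as-strata layout that measures change, each woman counts twice and the test is conservative if her answers correlate

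*SAP*

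**What the plan says.** The general rule is in the SAP, Outcomes measured at two or fewer time points. For a binary outcome, "a test of change in proportions for categorical outcomes, e.g. the Cochran-Mantel-Haenszel test, will be applied". Logistic regression with subject random effects is the alternative there when covariates are needed.

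The SAP's Primary Outcome section bases inference on a between-arm comparison of change from baseline to week 4 by a Cochran-Mantel-Haenszel (CMH) test. It adds: "This analysis tests for homogeneity of the odds ratio across strata (i.e. intervention and control". A test of the two week-4 proportions is ancillary.

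Secondary outcome 6 (three alcohol-knowledge items) has the same rule: "Analyses will be the comparison, between treatment groups, of change from baseline to 4-weeks post-randomisation using a Cochran-Mantel-Haenszel test".

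None of these sections defines the rows and columns of the 2x2 table.

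In protocol section 14.1, power is based on the proportion accurate. It takes the proportion of controls "who accurately identify alcohol as a clear risk factor for breast cancer is 0.22" and says the active proportion "is 12% greater at 0.34", "compensating for 20% attrition at follow-up". The result is 548 women (274 per arm) for 80% power.

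**The concern.** With the arms as strata, each arm's table must be built from the women's two visits. Two layouts are possible.

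- **A, visit by answer.** The odds ratio compares week 4 with baseline, so it measures change. Each woman contributes two observations to her arm's table. CMH and the standard homogeneity tests treat these as independent.
- **B, baseline answer by week-4 answer.** Each woman is counted once and the pairing is kept. The odds ratio then measures how strongly the two answers agree, not whether knowledge rose.

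Only A matches the SAP's description of a comparison of change. The same woman answering the same item four weeks apart will probably give positively correlated answers. If so, A overstates the variance of the change. The primary p-value and interval would then be conservative, and an effect of the planned size could be missed.

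The sentence on homogeneity adds to the ambiguity. CMH tests whether a common odds ratio equals 1; homogeneity is tested by Breslow-Day or an interaction term.

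**Working it through.** **Inputs from the documents.** Week-4 proportions 0.22 and 0.34, attrition 20% (protocol 14.1); "All statistical tests will be two-tailed, with alpha level set to 0.05" (protocol 14.2); "randomised at a 1:1 ratio" (protocol 6); 279 randomised per arm (SAP, Study rationale and design). Complete pairs: 279 × 0.80 ≈ 223 per arm.

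**Assumptions.** Baseline proportion 0.22 in both arms, taken equal to the control rate. Within-woman correlation ρ, shown from 0 to 0.56. The documents give neither.

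**Step 1. The plan's own figure.** Two independent proportions at week 4, pooled variance, no continuity correction:

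n = [1.96√(2 × 0.28 × 0.72) + 0.8416√(0.22 × 0.78 + 0.34 × 0.66)]² / 0.12² = 218.6, so 219 per arm. 219/0.80 = 273.75, so 274 per arm and 548 in all. This reproduces, with 80.1% power at 219. The sample size was therefore built on a week-4 comparison, not on a test of change.

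**Step 2. Layout A, log-odds scale, n = 223.**

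- Effect: ln(0.34/0.66) − ln(0.22/0.78) = 0.602.
- Per-woman variance terms: 1/(0.22 × 0.78) = 5.828 and 1/(0.34 × 0.66) = 4.456.
- SE with visits taken as independent: √[(3 × 5.828 + 4.456)/223] = √(21.94/223) = 0.314.
- True SE: √[(21.94 − 2ρ(5.828 + √(5.828 × 4.456)))/223] = √[(21.94 − 21.85ρ)/223].
- Power, pairing ignored: Φ[(0.602 − 1.96 × 0.314)/true SE].
- Power, pairing kept: Φ[0.602/true SE − 1.96].
- Actual two-sided size, pairing ignored: 2Φ[−1.96/√(1 − ρ)].

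| ρ | True SE | Power, pairing ignored | Power, pairing kept | Loss (points) | Actual size | Week-4 CMH stratified by baseline answer |
|---|---|---|---|---|---|---|
| 0 | 0.314 | 48.4% | 48.4% | 0 | 5.0% | 81% |
| 0.10 | 0.298 | 48.3% | 52.5% | 4 | 3.9% | 81% |
| 0.30 | 0.263 | 48.1% | 63.1% | 15 | 1.9% | 84–85% |
| 0.46 | 0.231 | 47.9% | 74.2% | 26 | 0.8% | 89% |
| 0.56 | 0.209 | 47.6% | 82.3% | 34–35 | 0.3% | 93% |

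The last column comes from simulation (20,000 trials per setting), where that test's size was about 5%. Simulation of the other columns agrees, with sizes of 4.8%, 3.8%, 1.9%, 0.8% and 0.3%.

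**Step 3. Splitting the shortfall.** At ρ = 0 the pairing costs nothing, yet power is already 48%. A difference in change carries the variance of four proportions instead of two. On the risk-difference scale that alone gives 55% at 223 per arm, against 81% for the week-4 comparison; the odds-ratio scale takes it to 48%. At ρ = 0.30 the gap to 80% is 32 points, of which about 15 come from ignored pairing and about 17 from testing change. At ρ = 0.56 ignored pairing accounts for all of it.

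**Step 4. The other readings.** Under layout B, a homogeneity test rejects about 5% of the time under the planned effect (4–7% for ρ from 0 to 0.7, 219 per arm). A literal CMH statistic on layout A tests change pooled over arms. It rejects 98–100% of the time when both arms rise equally from 22% to 34%, so it does not test the intervention.

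**The case against.** The strongest reply is that the SAP nowhere says the two answers are treated as independent. CMH is named only as an example in the general rule, the table is undefined, and the sentence on homogeneity already misdescribes CMH, so it cannot fix the layout with certainty. This stands, and the point is therefore conditional on layout A. It does not rescue the plan, because neither layout B nor the literal CMH statistic tests the intervention's effect on change.

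Three stronger readings are tempting, and the documents do not support them.

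- **That ignored pairing explains the fall from 80% to about 48%.** The whole fall is present at correlation 0. The pairing's share depends on a correlation that the documents do not give. Nor is the higher power of the stratified week-4 test due to restored pairing alone, since it also replaces a test of change.
- **That the two-visit binary exploratory outcomes ignore pairing by default.** The SAP's section on potential additional exploratory analyses offers mixed models for repeated measures, with the test of change as the bracketed alternative.
- **That the flaw could create a false-positive result.** Under layout A, with positive correlation, the homogeneity test errs in the conservative direction.

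The ancillary week-4 test of proportions also counts each woman once, matches the sample size and is unaffected. But it is not the basis for primary inference.

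**Conclusion.** The concern holds in conditional form. The firm defect is an undefined table for the primary outcome and secondary outcome 6. On the only arms-as-strata layout that measures change, each woman is counted twice, and the test is conservative if her answers are positively correlated. Power for the planned primary effect is then about 48% at every correlation tried. The part due to lost pairing runs from 0 points (ρ = 0) to about 34–35 (ρ = 0.56), with actual size falling from 5% to 0.3%. These figures rest on the assumed 22% baseline in both arms, 223 complete pairs per arm and the assumed correlations. Because this test governs the primary p-value, it should be settled before the result is interpreted.

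**What to change.** For the primary outcome and secondary outcome 6, use one row per woman: a CMH test of arm by week-4 answer (accurate or not), stratified by her own baseline answer, with the risk difference and 95% confidence interval. Logistic regression of the week-4 answer on arm and baseline answer is an acceptable alternative. Delete the sentence on homogeneity across arms.

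If the change formulation is kept, fit arm, time and arm × time by GEE with standard errors clustered on the woman. State its lower power, about 48–82% over the correlations above on the odds-ratio scale.

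Apply the same rule to two-visit binary exploratory outcomes wherever CMH would be used instead of a mixed model.

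The cost is SAP wording and a few lines of code; the data are already part of the planned assessments. There are two small downsides. The SAP is dated 18 February 2022, after the planned last follow-up in November 2021 (protocol 1.2), so the change needs a dated justification. The stratified test also uses only women with both answers, while protocol 14.2 includes all randomised women, so missing week-4 answers should be handled under the SAP's existing missing-at-random and imputation rule.
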